### 1.2 Specific Aims

Specific Aims of the R33 Enhanced Quality In Primary Care for Elders with Diabetes-ADRD (EQUIPED-ADRD) are:

- 1) Implement and evaluate a pragmatic trial in a large healthcare system using cluster randomization, and the practice change framework, that will: manage people with co-occurring DM and ADRD according to the guidelines developed to test our hypotheses and identify additional patients with cognitive impairment and inappropriate DM management.
- 2) Test whether EQUIPED-ADRD will increase the proportion of intervention patients who are in desirable glycemic and blood pressure ranges compared to control patients.
- 3) Test whether the EQUIPED-ADRD intervention will improve dyad perception of care quality and reduce treatment burden.
- 4) Test whether dementia symptoms will deteriorate less in intervention subjects compared to controls.

**Exploratory Aim.** Test whether intervention subjects will use fewer health care services than controls and will have less cognitive decline associated with desired changes in glycemic and blood pressure control.

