## 3. Subject Population

### 3.1 Total Number of Subjects and Sites

We will randomize the **20 largest NYU Langone Health primary care practices**, 9 Intervention (**INT**) clinics and 9 control (**CON**) clinics. We will enroll **1,000** patients (and their caregivers)  $\geq 65$  with diabetes (DM) and Alzheimers disease and other forms of dementia (ADRD) from these practices based on the Inclusion and Exclusion criteria below. As stated in inclusion and exclusion criteria, patients must have a caregiver who will also be enrolled. The patient and caregiver are referred to as a "dyad."

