## 7. Data Analysis

We will begin all analyses with descriptive summary statistics and graphical displays of all variables. Continuous variables will be summarized with means, medians, standard deviation and interquartile range; categorical variables will be summarized with frequencies. We will assess the balance by treatment assignment of patients in the INT and CON clinics with respect to demographic and clinical characteristics (e.g., age, gender, Charlson Index, socioeconomic status, baseline TBQ, etc.) using standard tests (t-tests, Wilcoxon rank-sum tests, and  $\chi^2$  tests as appropriate). Any factors that appear to be unbalanced by treatment assignment will be considered as adjustment factors in the primary analyses. All hypothesis testing will be two-sided and conducted using a significance level of 0.05.

The primary outcome of 'on target' HbA1C values will be measured for each patient as a binary indicator. The primary analysis will use a generalized linear mixed model approach, with a logit link, for the probability of being 'on target.' The treatment group (CON vs INT) will be the primary fixed effect of interest; we will also include the practice as a random effect to accommodate clustering of patients within clinics. We will also explore non-parametric methods such as quantile regression or other rank-based approaches. As noted above, randomization should obviate the need for any additional covariate adjustment, but we will explore whether adjustment for clinic-level characteristics (e.g., clinic size) and provider-level characteristics (e.g., provider demographics and panel size) is necessary. We will use standard assessments of goodness-of-fit, including residual plots, to evaluate the models. Finally, in addition to reporting the treatment difference in terms of the odds ratio from the logistic regression, we will report absolute risk difference as well.

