The secondary outcome of TBQ score, transformed into a binary outcome using an appropriate threshold (e.g., the median) will also be assessed using generalized logistic mixed models as described above; the treatment group (CON vs INT) will be the primary fixed effect of interest, with practice included as a random effect. As with the primary outcome, we will assess the need for adjustment using demographic or clinical characteristics, and will evaluate goodness-of-fit using standard approaches. We will also evaluate the TBQ as a continuous score using a linear mixed model. We will assess the validity of the linearity assumption, and seek a suitable transformation of the TBQ score if it appears to be violated. The statistical power for this analysis will be greater than that for the binary version of the outcome because of the additional information provided when using the scale in its original form.

Health care utilization outcomes will be analyzed using similar generalized linear mixed models; indicators of use will employ the logistic link function, and counts of days in various facility types will employ Poisson regression with the log link function. Treatment burden (using the Treatment Burden Scale) and dementia symptoms/cognitive function (using the DSRS) will also be evaluated as important secondary outcomes. We will have repeated assessments of these items at 6, 12, and 24 months, and will apply longitudinal mixed effects models to evaluate the trajectories and assess whether they differ by treatment group. Specifically, we will model time using indicator variables, and include interaction terms between time indicators and treatment group (CON vs INT); the statistical significance of the coefficients of the interaction terms will indicate whether

the trajectories in the outcomes over time differ by treatment group. We will also explore more parsimonious ways of modeling time, for example as a linear or polynomial effect. We will choose link functions that address ordinal outcomes, such as the log link for ordered categorical outcomes, in the context of proportional odds or multinomial logistic regression.

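### The primary test of the arm effect names no small-sample method for 18 (or 20) randomised clinics, so the stated 5% level is not secured

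*Combined protocol and SAP*

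**What the plan says.** The clinic is the randomised unit. Section 1.2 describes the aim as "Implement and evaluate a pragmatic trial in a large healthcare system using cluster randomization". Section 3.1 gives two counts in one sentence: the "20 largest NYU Langone Health primary care practices" are to be randomised, as "9 Intervention (INT) clinics and 9 control (CON) clinics". Section 4 also works with 9 intervention clinics. Section 1.1 sets 500 patients per group.

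Section 7 defines the primary outcome: "The primary outcome of 'on target' HbA1C values will be measured for each patient as a binary indicator". It fits a logit-link mixed model with arm as the fixed effect of interest, and "we will also include the practice as a random effect to accommodate clustering of patients within clinics". The level is fixed: "All hypothesis testing will be two-sided and conducted using a significance level of 0.05". The binary TBQ model has the same structure, "with practice included as a random effect", and the utilisation models are described as similar. Section 7 also leaves open adjustment for clinic-level and provider-level characteristics, and promises an absolute risk difference beside the odds ratio.

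Section 7 does not name an estimation method, a Wald, likelihood-ratio, t or F test, denominator degrees of freedom, a permutation test or a clinic-level analysis. Its sensitivity analyses concern missing data only. The documents give no ICC, expected on-target rate or variation in clinic size.

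**The concern.** Arm is assigned to clinics, so with 18 or 20 clinics only 16 or 18 between-clinic degrees of freedom inform the arm effect, however many patients are enrolled. The standard fit of a logistic mixed model estimates the clinic variance by maximum likelihood, which is biased low with few clusters, and then uses a normal or chi-square reference. Both make the p-value too small and the interval too narrow.

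Several tests with different error rates are compatible with the present text, so the choice could be made after the data are seen. Section 1.1 foresees wide dissemination if the programme succeeds, and the primary p-value would support that claim.

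**Working it through.** The plan has no power, ICC or type I error figure to reproduce, so the check asks what level the stated model delivers.

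**Inputs from the documents:** two-sided 0.05; binary outcome; random intercept for practice; K = 18 or 20 clinics; 1,000 patients, so 1,000/18 ≈ 56 or 1,000/20 = 50 per clinic. A variant with mean 35 uses the midpoint of the 20-50 diagnosed patients per clinic in Section 4.

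**Assumed, because not given:** latent-scale ICC 0 to 0.20; on-target rate 50-80%; coefficient of variation (CV) of clinic size 0 to 0.9.

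**Analytic check.** When between-clinic variation dominates, the arm estimate over its standard error follows approximately t with K - 2 - q degrees of freedom, q being the number of clinic-level covariates.
- Normal reference, unbiased variance: P(|t| > 1.96).
- Normal reference, ML variance: P(|t| > 1.96 × √((K - 2 - q)/K)).

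| K | q | df | Unbiased variance | ML cut-off | ML variance |
|---|---|---|---|---|---|
| 18 | 0 | 16 | 6.8% | 1.848 | 8.3% |
| 18 | 1 | 15 | 6.9% | 1.789 | 9.4% |
| 18 | 2 | 14 | 7.0% | 1.729 | 10.6% |
| 20 | 0 | 18 | 6.6% | 1.859 | 7.9% |
| 20 | 1 | 17 | 6.7% | 1.807 | 8.9% |
| 20 | 2 | 16 | 6.8% | 1.753 | 9.9% |

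**Simulation with no arm effect.** The random-intercept logistic model was fitted by ML with adaptive quadrature, 5,000 trials per scenario (Monte Carlo SE about 0.3-0.4 points). Each range covers two settings: 50% on target with equal clinics, and 60% on target with size CV 0.5.

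| Clinics (mean size) | ICC | Wald z | Likelihood ratio | Wald, t(K-2) | Clinic-proportion t-test |
|---|---|---|---|---|---|
| 18 (56) | 0.001 | 4.5-4.6% | 4.0-4.3% | 3.1-3.2% | 5.1-5.3% |
| 18 (56) | 0.01 | 6.2-6.7% | 5.2-5.9% | 4.2-5.0% | 4.5-5.0% |
| 18 (56) | 0.02 | 7.6-8.7% | 6.7-7.2% | 5.7-6.4% | 4.8-5.7% |
| 18 (56) | 0.05 | 7.9-8.2% | 6.4-6.7% | 5.6-6.2% | 4.4-4.9% |
| 18 (56) | 0.10 | 8.1-8.3% | 7.0% | 6.3-6.4% | 5.0-5.3% |
| 20 (50) | 0.01 | 6.4-7.2% | 5.4-6.3% | 4.7-5.2% | 4.9-5.2% |
| 20 (50) | 0.05 | 7.6-8.6% | 6.6-7.0% | 6.0-6.5% | 5.1-5.4% |
| 20 (50) | 0.10 | 7.8% | 6.6% | 5.9-6.2% | 4.9% |

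Further Wald z results for 18 clinics:
- mean size 35: 5.9% (ICC 0.01), 7.1% (0.02), 8.3-8.5% (0.05);
- size CV 0.9: 8.8% (ICC 0.05), 9.2% (0.10), 8.0% (0.20);
- ICC 0: 4.1%.

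Near-zero ICCs show no inflation because the clinic variance is then estimated as zero in about two-thirds of trials (64-67% at ICC 0.001 with 18 clinics). The model reduces to ordinary logistic regression, which is then nearly right.

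Smaller separate runs (1,000 to 3,000 trials per scenario) agree within wider error, with single unadjusted Wald z values up to 9.7%. In one of these (2,500 trials, 18 clinics, ICC 0.01-0.10), a single clinic-level covariate gave 8.0-10.0% and two gave 8.1-11.2%. This supports the analytic figures for q = 1 and 2.

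**Does changing only the reference suffice?** No. The ML Wald statistic referred to t(K-2) still rejected in 5.4-6.5% at ICC 0.02 or more with size CV up to 0.5, and in 6.3-7.4% with CV 0.9. The clinic-level t-test stayed at 4.4-5.7% in every scenario.

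**The case against.** The strongest reply is that the plan nowhere commits itself to a large-sample test. A mixed model with a practice random effect can be fitted and tested with an adequate small-sample correction, so the text is compatible with sound inference. A reader might infer that the primary analysis relies on a Wald z-test and therefore runs at a fixed 7-10%. The documents do not support that: they are silent on the test, and the rate depends on an ICC they do not give. It is about 5% or below near ICC zero and mostly 6-7% with a likelihood-ratio test at higher ICCs. No unadjusted scenario in the main simulation reached 10%. This part of the reply stands. It does not remove the gap, because nothing in Section 7 requires the adequate version.

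A reader might also extend the point to every secondary model. That goes too far. For the repeated outcomes, Section 7 tests arm-by-time interactions. With a clinic random intercept these are essentially within-clinic contrasts in which the clinic effect largely cancels, so clinics minus 2 is not the natural reference. They were not simulated. The continuous TBQ model is linear, so REML is available and the ML bias need not arise, although degrees of freedom still have to be stated.

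**Conclusion.** The point holds as a gap in specification with a measurable consequence. With 18 or 20 clinics, the default ML Wald z-test of the stated primary model would reject a true null in about 6-9% of trials for latent ICCs of 0.01-0.10, and a likelihood-ratio test in about 5-8%. If the ICC is near zero there is no inflation. Using the clinic-level adjustment that Section 7 permits raises the analytic Wald figure to 9.4-10.6% for one or two covariates with 18 clinics, or 8.9-9.9% with 20. These sizes rest on assumed ICCs, on-target rates and clinic-size variation, and on the default test being the one chosen. The conclusion covers the primary arm effect and, by the same structure, secondary models that test an overall arm effect with practice as a random effect. Only the primary model was quantified.

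**What to change.** First reconcile the 20 practices with the 9 + 9 clinics in Section 3.1, since the degrees of freedom are 16 or 18 accordingly. Then, before outcome data are examined by arm, name in Section 7 one small-sample method that supplies both the p-value and the confidence interval for the arm effect, for the odds ratio and the risk difference. Two choices are suitable:
- a clinic-level analysis with a t reference on (clinics - 2 - number of clinic-level covariates) degrees of freedom;
- a clinic-level permutation test that re-allocates clinics as they were actually randomised, with the interval obtained by inverting that test.

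State which effect scale carries the primary test, and fix any clinic-level covariates in advance. Do not simply refer the ML Wald statistic to a t distribution. Apply the same rule to the secondary models that test an overall arm effect; the arm-by-time tests are outside this point.

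The cost is a paragraph and a little code. Without clinic-level covariates, the t reference widens intervals by about 8% with 18 clinics (2.12/1.96 = 1.082) or 7% with 20 (2.101/1.96 = 1.072). Correcting the ML variance bias as well gives 1.082 × √(18/16) = 1.147 or 1.072 × √(20/18) = 1.130, so about 13-15% wider where between-clinic variation dominates.

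### Three treatment-burden analyses are planned and none is named as deciding: the TBQ cut-point, visit and baseline adjustment stay open, and perceived care quality has no planned model

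*Combined protocol and SAP*

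**What the plan says.** Section 7 (Data Analysis) describes three analyses of treatment burden.

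1. A binary one, presented first: "The secondary outcome of TBQ score, transformed into a binary outcome using an appropriate threshold (e.g., the median" is how it opens. The model has arm as the fixed effect and practice as a random effect.
2. A continuous one: "We will also evaluate the TBQ as a continuous score using a linear mixed model". The plan adds: "The statistical power for this analysis will be greater than that for the binary version of the outcome". If the linearity assumption fails, the analyst will "seek a suitable transformation of the TBQ score if it appears to be violated".
3. A longitudinal one: "Treatment burden (using the Treatment Burden Scale) and dementia symptoms/cognitive function (using the DSRS) will also be evaluated as important secondary outcomes", followed by "We will have repeated assessments of these items at 6, 12, and 24 months". Time enters as indicators with time-by-arm interactions, and simpler forms of time will be explored. The scale name differs from TBQ, but no other treatment-burden scale is described, so I read it as the TBQ.

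Table 1 (Section 5.4, Measures) schedules TBQ at baseline, 6, 12 and 24 months. In Section 7, baseline TBQ is named only among the balance-check variables: "socioeconomic status, baseline TBQ, etc.) using standard tests (t-tests, Wilcoxon rank-sum tests" and so on. Factors that look unbalanced will be considered for adjustment in the primary analyses. For TBQ the rule is "we will assess the need for adjustment using demographic or clinical characteristics".

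On perceived care quality, the outcome text in Section 5.4 labels it the main caregiver-reported outcome and lists it apart from treatment burden. Aim 3 (Section 1.2) also treats the two as separate. Table 1 has no row for it, the instrument list has no measure of it, and Section 7 has no model for it.

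**The concern.** A reader cannot tell which of the three analyses decides whether treatment burden improved. The cut-point, the visit, the transformation and the adjustment set can all still be chosen once outcomes by arm are visible. The form presented first is the one the plan itself calls weaker. Baseline TBQ, usually a useful covariate for a repeated score, is left to a balance test or an assessment of need. That balance test is an ordinary patient-level one, although clinics are what is randomized.

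Aim 3 also promises a test of perceived care quality that the analysis section does not contain.

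**Working it through.** **The plan's own figure.** There is none to reproduce. Section 7 says only that the continuous version has more power, so I checked the direction and size of that statement.

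**Inputs from the document.** Two-sided 0.05 (Section 7); 500 dyads per arm (Section 1.1); 9 clinics per arm (Section 3.1, which also says 20 practices, so 10 per arm is checked below).

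**Assumed, because the document gives no values.** Effect d = 0.2 to 0.4 SD; ICC 0.02 or 0.05; baseline-to-follow-up correlation 0.5; normal scores; no dropout.

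**Formulas.** Non-central t on 18 − 2 = 16 df.
- Continuous: variance of an arm mean = ICC/9 + (1 − ICC)/500.
- Median split: proportions Φ(±d/2); binary ICC = (2/π)·asin(ICC).
- Baseline-adjusted: the lower figure multiplies only the within-clinic part by 1 − 0.5² = 0.75 (equivalent to a clinic-level correlation of 0.25); the upper figure multiplies both parts (clinic-level correlation 0.5).

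**Worked case, d = 0.3, ICC 0.02.**
- Continuous: 0.02/9 + 0.98/500 = 0.004182; non-centrality 0.3/√(2 × 0.004182) = 3.28; power 86.8%.
- Split: proportions 0.5596 and 0.4404, difference 0.1192; binary ICC 0.01273; variance 0.5596 × 0.4404 × (0.01273/9 + 0.98727/500) = 0.000835; non-centrality 0.1192/√(2 × 0.000835) = 2.92; power 78.2%.
- Adjusted: variance 0.003692 or 0.003137; power 90.6 to 94.4%.

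| ICC | d | Split | Continuous | Continuous, adjusted |
|---|---|---|---|---|
| 0.02 | 0.2 | 44.6% | 53.8% | 59.0–66.0% |
| 0.02 | 0.3 | 78.2% | 86.8% | 90.6–94.4% |
| 0.02 | 0.4 | 95.5% | 98.4% | 99.2–99.7% |
| 0.05 | 0.2 | 30.1% | 33.7% | 35.6–42.8% |
| 0.05 | 0.3 | 57.8% | 63.6% | 66.4–75.9% |
| 0.05 | 0.4 | 82.1% | 86.7% | 88.8–94.4% |

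With 10 clinics per arm and d = 0.3, split and continuous are 80.5 and 89.0% (ICC 0.02) and 61.2 and 67.6% (ICC 0.05). With 20% loss they are 72.6 and 83.0%, and 54.3 and 60.9%. If TBQ is strongly right-skewed and left untransformed, simulation gives 78.1 against 82.0% and 57.9 against 60.7%.

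**Balance test.** Suppose baseline TBQ is flagged when a patient-level t-test gives p < 0.05. With 500/9 = 55.6 dyads per clinic, the design effect is 1 + 54.6 × 0.02 = 2.09 or 1 + 54.6 × 0.05 = 3.73. The chance of a flag is then P(|Z| > 1.96/√2.09) = 18% or P(|Z| > 1.96/√3.73) = 31%, rather than 5%.

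**Open visit and cut-point.** With no true effect and inter-visit correlation 0.5 to 0.7, simulation puts the chance that the median split reaches 0.05 at one or more of three visits at 12–13%. With the 40th, 50th and 60th percentiles also open it is 19–23%.

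**Baseline measured after contact.** If the intervention arm's baseline has already moved 0.1 SD in the direction of benefit and the slope is 0.5, the adjusted effect is 0.3 − 0.5 × 0.1 = 0.25 SD. Adjusted power is then 78–84% against 87% unadjusted (ICC 0.02), and 51–60% against 64% (ICC 0.05).

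**Perceived care quality.** No arithmetic applies. Sections 1.2 and 5.4 promise the outcome, and Section 7 omits it.

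**The case against.** Section 7 states no hierarchy. That the split leads is inferred from its position and from the continuous model being added as a further analysis. The full score is analysed too, and twice if the longitudinal model counts. A reader might infer that the trial throws the score away, but the text does not support that. What stands is that no analysis is named as deciding.

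A reader might also take 12–23% as the trial's false-positive rate, or 18% and 31% as the behaviour of its adjustment rule. Neither follows. The plan does not say that the best result will be picked, and it contains no p < 0.05 trigger. The figures show only what the open wording allows.

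The most tempting remedy, always adjusting for baseline at a single visit, goes too far for two reasons.

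- **Timing.** The baseline interview follows consent (E3). Panel-manager contact follows the clinic appointment (Section 4), and the panel manager does not know who has consented (Sections 6.2 and 10.1). Dyads added later may join clinics that are already active. The document therefore does not ensure that baseline precedes contact. Adjustment also gains nothing at ICC 0.02, and loses about 5 points at 0.05, if clinic means at baseline and follow-up are unrelated.
- **Refreshed sample.** Late entrants are followed for shorter periods, so a model confined to one late visit would drop some of them. The longitudinal model already planned uses every visit.

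Finally, the survey instrument is a separate document that Section 5.4 refers to and that I have not seen. It would be wrong to conclude that perceived care quality is not collected. The caregiver global health scale also has no Table 1 row, yet it is described in the instrument list. Only the missing analysis is certain.

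**Conclusion.** The concern holds in this form: three unranked treatment-burden analyses, with an open cut-point, no fixed visit or contrast, and baseline TBQ left to need or imbalance. The plan's statement that the continuous score has more power is confirmed in direction. The gain is about 3 to 9 points at ICC 0.02 and about 4 to 6 points at ICC 0.05, and smaller if TBQ is skewed and untransformed. Any further gain from baseline adjustment depends on the clinic-level correlation and on when baseline was measured. All power figures rest on assumed effects, ICCs and correlations.

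The missing model for perceived care quality is a separate gap between Sections 1.2, 5.4 and 7, and none of these figures bears on it. TBQ is a secondary outcome, so the primary HbA1c result is untouched. This should be corrected, but it does not threaten the trial.

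**What to change.** 1. Make the continuous TBQ score the main treatment-burden analysis, taken from the longitudinal mixed model already planned, with a practice random effect and a patient-level effect for repeated visits. Name one treatment contrast, and settle any transformation, before outcomes are compared by arm. Confirm that the scale named in that paragraph is the TBQ.
2. Report the binary version as supportive at a cut-point fixed in advance, and the other visits as secondary.
3. Include baseline TBQ by pre-specification, not after a balance test, where the baseline survey preceded panel-manager contact. Report a sensitivity analysis without baseline adjustment, because a baseline taken after contact may already reflect the intervention, and adjusting would then remove part of the effect.
4. Reconcile Aim 3, the outcome text in Section 5.4 and Section 7 on perceived care quality. If the survey contains items, state the score, contrast and model. If not, remove the main-outcome label and that part of Aim 3.

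The cost is mostly wording: TBQ is already scheduled at all four visits and the models are already planned. Item 3 also needs the dates of the baseline survey and of first panel-manager contact to be compared. Two downsides remain: a care-quality claim may have to be dropped, and the TBQ is still being validated for caregivers (Section 5.4).
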